4 STUDY DRUG

Study drug includes both Investigational [Medicinal] Product (IP/IMP) and Non-investigational [Medicinal] Products (Non-IP/Non-IMP) and can consist of the following:

- All products, active or placebo, being tested or used as a comparator in a clinical trial.
- Study required premedication, and
- Other drugs administered as part of the study that are critical to claims of efficacy (eg, background therapy, rescue medications)
- Diagnostic agents: (such as glucose for glucose challenge) given as part of the protocol requirements must also be included in the dosing data collection.

All protocol-specified investigational product and non- investigational products are considered study drug. See [Table 4-1](#) for product description of elotuzumab, lenalidomide and dexamethasone.

Table 4-1: Study Drugs for CA204116 Treatment Period

Product Description / Class and Dosage Form	Potency	IP/Non-IMP	Blinded or Open Label	Packaging/ Appearance	Storage Conditions (per label)
Elotuzumab Powder for Solution for Infusion	400 mg/vial	IP	Open Label	20 mL Vial/ Sterile, white to off-white, preservative-free, lyophilized cake	Store at 2° - 8 °C
Lenalidomide (Revlimid®)capsule	5 mg, 10 mg, 15 mg and 25 mg	IP	Open Label	21 capsules per bottle	Store at 15° - 25°C.
Dexamethasone Tablets	2 mg and 4 mg & various strengths	Non-IMP	NA	Various	Refer to label on container or package insert/summary of product characteristics
Dexamethasone Solution	4 mg/mL, 8 mg/mL & various strengths	Non-IMP	NA	Various	Refer to label on container or package insert/summary of product characteristics

Elotuzumab and lenalidomide will be supplied by the BMS. Dexamethasone tablets and solution for IV infusion will be obtained by the investigating site's standard prescribing procedures.

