4.5.4.3 Lenalidomide

Dose adjustments, as summarized below, are recommended for the management of NCI CTCAE Grade 3 and 4 toxicities for thrombocytopenia, neutropenia or other toxicities that are judged by the investigator to be related to lenalidomide. Information in Table 4.5.4.3-1 and Table 4.5.4.3-2 is based on current standard of clinical practice.

Table 4.5.4.3-1: Treating Thrombocytopenia Related to Lenalidomide

When Platelet Counts:	Recommended Course
Fall to < 30,000/mm ³	Interrupt lenalidomide treatment; follow complete blood counts weekly.
Return to ≥ 30,000/ mm ³	Resume lenalidomide at 15 mg, Days 1 - 21, once daily.
For each subsequent drop < 30,000/ mm ³	Interrupt lenalidomide treatment.
Return to ≥ 30,000/ mm ³	Resume lenalidomide at 5 mg less than previous dose, Days 1 - 21, once daily. Do not dose below 5 mg.

Table 4.5.4.3-2: Treating Neutropenia Related to Lenalidomide

When Neutrophil Counts:	Recommended Course
Fall to < 1000/ mm ³	Interrupt lenalidomide treatment, add G-CSF; ^a follow complete blood counts weekly.
Return to ≥ 1000/ mm ³ and neutropenia is the only toxicity	Resume lenalidomide at 25 mg, Days 1 - 21, once daily.
Return to ≥ 1000/mm ³ and if other toxicity	Resume lenalidomide at 15 mg, Days 1 - 21, once daily.
For each subsequent drop < 1000/ mm ³	Interrupt lenalidomide treatment.
Return to ≥ 1000/ mm ³	Resume lenalidomide at 5 mg less than previous dose, Days 1 - 21, once daily. Do not dose below 5 mg.

In case of neutropenia, consider the use of growth factors in subject management.

^a G-CSF = Granulocyte Colony-Stimulating Factor

Lenalidomide Dose Adjustments in Subjects with Renal Impairment

Since lenalidomide is primarily excreted via the kidney, adjustments to the dose of lenalidomide are provided based on the lenalidomide country prescribing information. The regimen of 21-day dosing every 28 days remains the same despite the dose reductions described below.

Table 4.5.4.3-3: Lenalidomide Dose Adjustments in Subjects with Renal Impairment

Creatinine Clearance (CrCl):	Recommended Course
Moderate renal impairment (30 ≤ CrCl < 60 mL/min)	10 mg, every 24 hours
Severe renal impairment (CrCl < 30 mL/min, not requiring dialysis)	15 mg every 48 hours
End Stage Renal Disease (CrCl < 30 mL/min, requiring dialysis)	5 mg once daily. On dialysis days, dose should be administered following dialysis

Source: Lenalidomide USPI

Dose Adjustments During Treatment for Other Grade 3 and 4 Toxicities

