A by-subject listing for dose omission will be presented for all treated subjects. This listing will include all reported omissions per CRF, regardless of whether the subject had a computed omission based on the actual dosing dates.

- **Dose Interruption**

The number and percentage of subjects with any interruption in their elotuzumab infusion, with 1, 2, 3, or ≥ 4 interruptions, with an interruption due to “infusion reaction”, “infusion administration issues” and “other” will be presented. In addition, duration of interruptions (in minutes) will be summarized via descriptive statistics.

A by subject listing will be generated for elotuzumab IV interruptions. This listing will include reason for interruption, whether the infusion was resumed, and duration of the interruption.

- **IV Rate Reduction**

The number and percentage of subjects with any elotuzumab IV rate reduction, with 1, 2, 3, or ≥ 4 rate reductions, and with rate reductions due to “infusion reaction,” “infusion administration issues,” and “other” will be presented.

A by subject listing will be generated for elotuzumab IV rate reductions.

Lenalidomide

- **Dose Reduction**

Reduction of Lenalidomide will be computed based on the actual dose received. In any study day (excluding, cycle 1, day 1), the drug will have a calculated reduction compared to the previous day, if the actual level of the administered dose is below the actual level of the administered dose in the previous instance. The information for this analysis will be derived programmatically, using the total daily dose on the “Record of Study Medication - lenalidomide” eCRF page.

The daily dose levels are defined as follows:

Dose level 0 or full dose (25 mg): ≥ 20.0

Dose level -1 (15 mg): 12.5 mg to < 20.0

Dose level -2 or starting dose for moderate renal impairment (10 mg): 8.75 to < 12.5 mg

Dose level -3 for subjects with severe renal impairment (15 mg every 48 hours): 6.25 to < 8.75 mg

Dose level -4 for subjects with End Stage Renal Disease (ESRD) (5 mg): < 6.25 mg

The number and percentage of subjects with a dose reduction, and the lowest dose level achieved per subject (-1, -2, -3, \leq -4), will be presented by treatment group. This table will be broken out by whether the subject started at the standard dose level or at the 10 mg dose level.

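### The SAP bands lenalidomide level -3 on a 48-hour average but assigns levels from each day's dose, so the stated rule misclassifies 15 mg every 48 hours

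*SAP*

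**What the plan says.** SAP 7.4.1.2 (Lenalidomide, Dose Reduction) works day by day: "In any study day (excluding, cycle 1, day 1), the drug will have a calculated reduction compared to the previous day". The test sets each administered dose against the one before it, and a reduction is counted "if the actual level of the administered dose is below the actual level of the administered dose in the previous instance". The information is "derived programmatically, using the total daily dose on the" lenalidomide study-medication eCRF page. The section gives no averaging over a dosing interval and no rule for days without drug.

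Five daily levels are then banded. Level 0 (25 mg) is 20.0 mg or more. The next two are "Dose level -1 (15 mg): 12.5 mg to < 20.0" and, one step lower, "Dose level -2 or starting dose for moderate renal impairment (10 mg): 8.75 to < 12.5 mg". The fourth is "Dose level -3 for subjects with severe renal impairment (15 mg every 48 hours): 6.25 to < 8.75 mg". Level -4 (5 mg) is anything below 6.25 mg. The table shows how many subjects had a reduction and the lowest level each reached, split by standard or 10 mg starting dose. Reasons are tabulated for calculated reductions. A listing keeps every reduction that the investigator reported, calculated or not.

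Protocol Table 4.5.4.3-3 gives "15 mg every 48 hours" for severe renal impairment and 10 mg every 24 hours for moderate impairment, within the usual 21 days of each 28-day cycle. Protocol Table 4-1 lists capsules of "5 mg, 10 mg, 15 mg and 25 mg", and Protocol 4.5.1 requires them to be taken intact.

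**The concern.** The band and the assignment rule use different quantities. The band describes an average over two days; the rule reads one day at a time. A dosing day on the 48-hour schedule reads 15 mg, which is level -1, and an off day has either no record or a zero. Neither is level -3.

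The table would then misstate dose reduction for subjects whose renal function worsens on study. It could also disagree with the relative dose intensity table in SAP 7.4.1.3, which would show the loss of dose while the reduction table shows no step down.

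**Working it through.** **Inputs.** Band limits, per-day rule and data source: SAP 7.4.1.2. Capsule strengths: Protocol Table 4-1. Capsules intact: Protocol 4.5.1. Renal schedules and 21-day dosing: Protocol 4.5.4.3. Planned weekly doses of 131.25 and 52.5 mg: SAP 7.4.1.3.

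**1. Reproduce the SAP limits.** Take the nominal doses as 25, 15, 10, 7.5 and 5 mg/day, where 7.5 = 15/2. The midpoints are

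- (25 + 15)/2 = 20.0
- (15 + 10)/2 = 12.5
- (10 + 7.5)/2 = 8.75
- (7.5 + 5)/2 = 6.25

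All four match the SAP exactly. The level -3 band is therefore built on the 48-hour average.

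**2. Band the possible daily totals.** Intact capsules of 5, 10, 15 and 25 mg give only multiples of 5 mg.

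| Daily total (mg) | 0 | 5 | 10 | 15 | 20 | 25 |
|---|---|---|---|---|---|---|
| Level | -4 | -4 | -2 | -1 | 0 | 0 |

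No total falls in 6.25 to <8.75.

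**3. Apply the rule to a change of schedule.** Take 21 days at the old dose, then 21 scheduled days of 15 mg every 48 hours starting on the first day (11 dosing days, 10 off days). The rest week is left out. Each cell gives the number of calculated reductions and the lowest level.

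| Changing from | Dosing days only | Off days stored as 0 mg | 7.5 mg/day average |
|---|---|---|---|
| 10 mg daily (level -2) | 0; lowest -2 | 10; lowest -4 | 1; lowest -3 |
| 15 mg daily (level -1) | 0; lowest -1 | 10; lowest -4 | 1; lowest -3 |
| 25 mg daily (level 0) | 1; lowest -1 | 11; lowest -4 | 1; lowest -3 |

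Only the last column gives the level that the SAP label names. Averaging the actual 21 days gives 11 × 15/21 = 165/21 = 7.86 mg/day, also level -3.

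**4. Size of the real change in dose.**

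- 25 mg daily: 25 × 21/4 = 131.25 mg/week
- 10 mg daily: 10 × 21/4 = 52.5 mg/week
- 15 mg every 48 hours, 10.5 doses per cycle on average: 7.5 × 21/4 = 39.4 mg/week
- 15 mg every 48 hours, 11 doses when started on Day 1: 15 × 11/4 = 41.25 mg/week

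From 10 mg daily the cut is 1 - 41.25/52.5 = 21% to 1 - 39.4/52.5 = 25%. From 25 mg daily it is 1 - 41.25/131.25 = 69% to 1 - 39.4/131.25 = 70%.

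For a subject who started at 10 mg, a cycle on the 48-hour schedule runs at 75% to 79% of the planned weekly dose, while under the dosing-days reading the reduction table counts nothing for the change.

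**The case against.** The strongest reply is that the intent is plain. The limits are exact midpoints around 7.5 mg/day, so the author meant average mg/day for that row, and a programmer might read it so. The eCRF page and its completion guidance are not in the documents; if a 48-hour regimen is entered or derived there as 7.5 mg/day, level -3 is reached. This stands as a condition on the conclusion. It does not rescue the text, because the stated rule is per day, is based on dose actually received, and contains no conversion.

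The true loss of exposure is also captured elsewhere. Cumulative dose, dose intensity and relative dose intensity (SAP 7.4.1.3) do not use the bands, and the listing keeps investigator-reported reductions. This stands too, and it keeps the point small.

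The off-days-as-zero reading is the less natural one. The SAP compares administered doses, and zeros in the Day 22-28 rest week would put every subject at level -4. It is shown because the SAP does not exclude it.

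A reader might infer three stronger things that the documents do not support:

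- *The change from 10 mg daily is reported as a dose increase.* The level moves from -2 to -1, but the SAP defines and tabulates no increases. The change simply goes uncounted.
- *The level -3 row must always be zero.* That depends on the unseen eCRF field.
- *Subjects with the worst renal function will appear the least reduced.* With zeros stored they would show level -4. On dosing days only, a subject who went from 25 mg to 10 mg and then to 15 mg every 48 hours keeps lowest level -2 and one counted reduction. Only a direct change from 25 mg shows -1.

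**Conclusion.** The derivation is wrong as written, and the point is minor. The level -3 limits describe a 48-hour average; the rule that assigns levels uses single-day totals, none of which can fall within those limits with intact capsules. Depending on how off days are stored, the change to 15 mg every 48 hours is missed, understated or counted many times over.

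This rests on the eCRF field holding the dose taken on each day. If it holds an average, the table comes out as intended, though the SAP should still say so.

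The reach is narrow. Creatinine clearance below 30 mL/min is an exclusion (Protocol 3.3.2, criterion 3g), so only subjects who fall below it on study and move to this schedule are affected. The documents give no number; it is probably few and may be none. The reduction count, the lowest-level table and the tabulated reasons are affected. Dose intensity, the investigator-reported listing, ORR and PFS are not.

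**What to change.** Add one sentence to SAP 7.4.1.2: for alternate-day dosing, the level is assigned from the mean mg/day over the dosing interval (dose divided by 2), and planned off days are excluded from the comparison with the previous instance. Then 15 mg every 48 hours maps to 7.5 mg/day and level -3, and a change to it from 10, 15 or 25 mg daily counts as one reduction.

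Check first what the eCRF daily-dose field holds. If it already stores 7.5 mg, the conversion must not be applied again, since 7.5/2 = 3.75 mg would fall in level -4.

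The cost is one sentence and a small change to the derivation program. No new data are needed if the record shows dosing dates or frequency. This concerns the derivation only and takes no view on the dose or schedule.

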4.5.3 Dose Delay or Interruption

If the dose of one drug in the regimen (ie, lenalidomide, dexamethasone or elotuzumab) is delayed or interrupted, the treatment with the other drugs may continue as scheduled. Subjects experiencing a 28-day delay in all study drugs lenalidomide, dexamethasone, and elotuzumab due to an adverse event(s) related to study treatment must be discontinued from study drug. Subjects experiencing delays unrelated to study therapy, for example due to radiation therapy may delay study treatment up to 42 days. Delays greater than 28 days must be discussed with the medical monitor.

Each cycle is 28 days. While dose delays or interruptions are permitted, the start of each cycle cannot be delayed and is fixed relative to Cycle 1 Day 1. Adjustments to the Cycle 1 Day 1 anchored schedule should not be performed. Missed doses should be skipped, not delayed, if not given within the allowed window.

Subjects may continue on study therapy even if components of the study therapy must be discontinued. For example, a subject on lenalidomide and dexamethasone may continue on study therapy even if dexamethasone must be discontinued for an adverse event. Likewise, a subject on

the investigational arm may continue on study therapy if elotuzumab must be discontinued for an adverse event or other reason. Patients are considered still on study therapy even if they continue solely on lenalidomide.

Please consult the BMS medical monitor or any questions regarding dose interruption or study therapy discontinuation.

4.5.3.1 *Elotuzumab*

In Cycle 1 and 2, an elotuzumab dose that falls outside of the pre-specified window (-1 to +3 days) must be skipped.

In Cycles 3 and beyond, elotuzumab dosing may be delayed for up to 1 week. If unable to administer within 1 week, then the dose should be skipped and resumption of the elotuzumab continues per the protocol defined schedule.

4.5.3.2 *Dexamethasone*

Dexamethasone delay should be performed as clinically indicated at the discretion of the investigator.

For subjects receiving elotuzumab, the weekly dexamethasone dose that coincides with or is temporally closest to the elotuzumab dosing must be administered as part of the premedication for elotuzumab per the guidance in [Section 4.5.1](#).

4.5.3.3 *Lenalidomide*

Lenalidomide delay should be performed as clinically indicated at the discretion of the investigator.

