Premedication for Elotuzumab (Investigational arm only)	X	X	X	X		
Elotuzumab Infusion (Investigational arm only)	X	X	X	X		In Cycles 1 and 2, an elotuzumab dose that falls outside of the pre-specified window (-1 to +3 days) must be skipped.
Lenalidomide Administration	Day 1 - 21 of each cycle					
Dexamethasone Administration	X	X	X	X		
Dispense Lenalidomide	X					Dispense lenalidomide on Day 1 of cycle per the Revlimid Risk Management Plan

^a For the patients who discontinue in Cycle 1 or 2, the procedure of "End of Treatment" and "Post End of Treatment" in Table 5.1-3 must be applied.

Table 5.1-3: Long-term Procedural Outline (CA204116) Cycles 3 and Beyond

Procedure	Day 1	Day 8	Day 15	Day 22	Rest Day 23 - 28	End of Treatment	Days 30 & 60 Post End of Treatment ^a	Notes
Safety Assessments								
Targeted Physical Examination	X					X		Perform up to 3 days prior to dosing, include weight (Section 5.4.1)
Vital Signs	X		X*			X		Measure vital signs prior to administration of premedication, pre-elotuzumab infusion, 30 minutes after the start of elotuzumab infusion, at the end of infusion, and 30 minutes after the completion of elotuzumab infusion. Control arm measure vital signs once at each visit. *Not required in Cycles 19 and beyond
Performance Status (ECOG)	X					X		Evaluate prior to dosing
Serious Adverse Events Assessment	X		X*			X	X	Evaluate prior to dosing *Not required in Cycles 19 and beyond All SAEs must be collected that occur within 60 days of discontinuation of dosing
Adverse Events Assessment	X		X*			X	X	Evaluate prior to dosing *Not required in Cycles 19 and beyond
Second Primary Malignancy	X					X	X	Section 6.7 Performed at 30 and 60 day ± 1 week EOT follow up visits.
Concomitant Medications	X		X*			X	X	Evaluate prior to dosing *Not required in Cycles 19 and beyond

Table 5.1-3: Long-term Procedural Outline (CA204116) Cycles 3 and Beyond

Procedure	Day 1	Day 8	Day 15	Day 22	Rest Day 23 - 28	End of Treatment	Days 30 & 60 Post End of Treatment ^a	Notes
Laboratory Test for Safety								
CBC, differential, platelets	X					X		Can be drawn up to 3 days prior to study visit. (Section 5.4.4)
Serum Chemistry	X					X		Can be drawn up to 3 days prior to study visit. (Section 5.4.4) Serum calcium and albumin every 4 weeks from date of first dose of study drug until disease progression, even if subject is on subsequent therapy.

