6.2 Treatment Regimens

Subjects will be randomized to one of two treatment arms, ELd or Ld. Subjects will receive these treatments in 28-day cycles until disease progression, unacceptable toxicity or withdrawal of consent.

On ELd arm subjects receive:

- Elotuzumab: 10mg/kg intravenous (IV) on Days 1, 8, 15 and 22 of the cycle during Cycles 1 and 2; Days 1 and 15 during Cycles 3-18 and 20mg/kg intravenous (IV) on Day 1 of the cycle during subsequent cycles.
- Lenalidomide: 25mg orally (po) on Days 1-21 of each cycle.
- Dexamethasone: Administered on Days 1, 8, 15 and 22 of cycle. 28mg po + 8mg IV whenever given prior to elotuzumab; 40mg po on weeks on which no elotuzumab is given.

On Ld arm subjects receive:

- Lenalidomide: 25mg po on Days 1-21 of each cycle.
- Dexamethasone: 40mg po on Days 1, 8, 15 and 22 of each cycle.

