The reason for dose reduction as reported by the investigator will be tabulated for all instances with a calculated reduction based on the dose modification for Lenalidomide page. A category “unknown” will be defined for all calculated reductions with no reason reported by the investigator.

A by-subject listing of dose reductions will be generated. This will include all reported reductions per investigator, regardless of whether it met the requirements for a calculated reduction.

- **Dose Interruption**

In any cycle, the Lenalidomide dose will be considered as interrupted if there is a gap of two or more days between two dosing dates within that cycle where the subject did not receive the study drug. This will be calculated based on the information from the dose modification CRF for Lenalidomide.

The number and percentage of subjects with dose interruption, with 1, 2, 3, or ≥ 4 reported interruptions will be presented. For subjects with a computed interruption, their reason for

interruption will be summarized from the dose modification CRF. For subjects without an available reason for interruption, the category “unknown” will be used.

Dexamethasone (IV) and Oral

For IV dexamethasone the following summaries will be provided:

- The number of subjects with any dose delay, with 1, 2, 3, or ≥ 4 reported delays, and with a reason for delay of “hematologic toxicity”, “non-hematologic toxicity”, “AE”, “dosing error” and “other”.
- The number of subjects with any reported dose omission, with 1, 2, 3, or ≥ 4 reported omissions, and with a reported reason for omission of “hematologic toxicity”, “non-hematologic toxicity”, “AE”, “dosing error” and “other”.
- The number of subjects with any reduction in the dose of the drug, and with a reason for the reduction of “hematologic toxicity”, “non-hematologic toxicity”, “AE”, “dosing error”, and “other”).

For PO dexamethasone the following summaries will be produced:

- The number of subjects with any dose modification, with 1, 2, 3, or ≥ 4 reported modifications, and with a reason for the modification of “hematologic toxicity”, “non-hematologic toxicity”, “AE”, “dosing error” and “other”).

By subject listings of record of study medication for each of IV dexamethasone and PO dexamethasone will be provided.

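### The SAP's computed lenalidomide interruption needs a dose on both sides of the gap within one cycle, so the interruption table undercounts holds, and long holds most

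*SAP*

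**What the plan says.** The SAP's schedule (6.2) is "Lenalidomide: 25mg orally (po) on Days 1-21 of each cycle". Under Protocol 4.5.3, "the start of each cycle cannot be delayed and is fixed relative to Cycle 1 Day 1", and doses not given in time are skipped rather than moved.

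For lenalidomide, SAP 7.4.1.2 calls a cycle interrupted "if there is a gap of two or more days between two dosing dates within that cycle". On the data source it says: "This will be calculated based on the information from the dose modification CRF for Lenalidomide". The table is described as subjects "with 1, 2, 3, or ≥ 4 reported interruptions will be presented", while the sentence on reasons begins "For subjects with a computed interruption".

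For elotuzumab, the same section defines delays and omissions by the interval between infusions, which can cross cycles. It also lists every reported delay or omission, whether or not the computed rule was met. Lenalidomide reductions get the same kind of listing. Lenalidomide interruptions get none, and there is no separate lenalidomide delay or omission rule.

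On when holds arise, Protocol Table 4.5.4.3-1 says of low platelets: "Interrupt lenalidomide treatment; follow complete blood counts weekly". Blood counts are scheduled on Days 1, 8, 15 and 22 in Cycles 1-2 (Table 5.1-2). In "Table 5.1-3: Long-term Procedural Outline (CA204116) Cycles 3 and Beyond" the only scheduled on-treatment count is on Day 1.

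**The concern.** A gap between two doses of the same cycle can be seen only if the subject took lenalidomide both before and after the hold in that cycle. Because cycle starts are fixed, a hold that begins on Day 1 has no earlier dose in its cycle. A hold that reaches Day 21 normally has no later one, and a skipped cycle has no doses at all. None of these meets the definition.

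The protocol makes such holds foreseeable. From Cycle 3, a hold prompted by the scheduled blood count starts on Day 1. Weekly counts after an interruption point to holds of about a week or more, and Protocol 4.5.3 contemplates study-drug delays of 28 days, or up to 42 days when unrelated to therapy.

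At stake is a correct count of how often the backbone drug was held in each arm, and why. SAP section 5 says results from both arms will help assess what elotuzumab adds to Ld. A table that keeps short mid-cycle gaps and drops long holds is a poor description for that purpose.

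**Working it through.** **Inputs.** Planned dosing on Days 1-21 of 28 (SAP 6.2); fixed cycle starts and skipped doses (Protocol 4.5.3); the interruption rule (SAP 7.4.1.2); planned lenalidomide dose intensity of 131.25 mg/week, or 52.5 mg/week for subjects starting at 10 mg (SAP 7.4.1.3).

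**Schedule check.** 25 × 21/28 × 7 = 131.25 mg/week and 10 × 21/28 × 7 = 52.5 mg/week. Both match the SAP, so Days 1-21 is the schedule it works from.

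**Detection condition.** Let s be the first missed day (1 to 21) and L the hold length in calendar days, with dosing otherwise complete and no dose on Days 22-28. A dose before the hold in the same cycle needs s ≥ 2. A dose after it in the same cycle needs s + L ≤ 21. The start days that are detected run from 2 to 21 − L, which is 20 − L of 21 (none when L ≥ 20).

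| Hold length L | Start days flagged | Start days missed |
|---|---|---|
| 2 days | 18/21 (86%) | 3/21 |
| 3 days | 17/21 (81%) | 4/21 |
| 7 days | 13/21 (62%) | 8/21 (38%) |
| 14 days | 6/21 (29%) | 15/21 (71%) |
| 19 days | 1/21 (5%) | 20/21 |
| 20 days or more | 0/21 | 21/21 |

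The counts are the same whether the two-day gap means two missed days or two dates that differ by two.

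**Single holds in four cycles (84 planned doses).**
- Days 8-14: 7 doses missed, flagged.
- Days 1-7 or Days 15-21: 7 missed, not flagged.
- Days 1-14: 14 missed, not flagged.
- Day 15 of one cycle to Day 7 of the next: 14 missed, not flagged.
- Whole cycle: 21 missed, not flagged.

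**What relative dose intensity (RDI) still shows.** Dose intensity is 7 × cumulative dose / days, with 4 × 28 = 112 days here.
- Whole cycle missed: 7 × (63 × 25)/112 = 98.44 mg/week; 98.44/131.25 = 0.75.
- 14 doses missed: 7 × (70 × 25)/112 = 109.375 mg/week; RDI 0.833.
- 7 doses missed: 7 × (77 × 25)/112 = 120.31 mg/week; RDI 0.917, still in the SAP's top band (90% or more).

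**What a calendar count would recover.** Suppose two or more consecutive scheduled days without a dose were counted, before any tolerance at cycle start. All 15 missed fourteen-day holds would be captured. So would 7 of the 8 missed seven-day holds: the one starting on Day 21 covers Days 21-27 and misses a single scheduled dose.

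**The case against.** The strongest reply is that the SAP shows these holds elsewhere. Cumulative dose, dose intensity and RDI bands are presented by treatment group (7.4.1.3). The number of subjects taking each drug in each cycle is summarised (7.4.1.1), so a wholly skipped cycle lowers a visible count, although discontinuation lowers it too. Protocol 6.3 requires a laboratory abnormality that led to interruption to be recorded as an adverse event, and SAP 7.6.1 and 7.6.6 tabulate adverse events and worst-grade neutrophils and platelets. This stands. A reader might infer that such holds leave no trace, or that a between-arm difference in long holds would be hidden. The documents do not support that. These summaries do not, however, give a number of hold episodes or a reason for each. RDI also mixes holds with reductions.

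A second reply is that the table is said to show reported interruptions, so a Day 1 hold entered by the investigator might be counted. That is possible, and how the CRF records holds cannot be seen. But the elotuzumab paragraph uses the word reported for delays it has just defined by computation, and the next lenalidomide sentence says computed. The wording does not clearly override the definition.

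Third, a reader might take lenalidomide interruption to be a main tolerability comparison. No section says so, and SAP section 5 plans no formal comparison between arms.

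Fourth, the uniform start day is illustrative, and the documents give no hold frequencies. In Cycles 1-2, a hold begun on the Day 8 count and ended on Day 15 is flagged. The share of real holds missed therefore cannot be estimated.

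Finally, a calendar rule could create false interruptions. Lenalidomide is dispensed at the Day 1 visit, and Table 4.5.1-1 shows a window of -1 to +3 days. This objection is sound, and the remedy has to allow for it.

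**Conclusion.** The point holds within limits. Read literally, the computed definition omits holds that start on Day 1, reach Day 21, cross a cycle boundary or fill a cycle, and detection falls steadily as the hold lengthens. Two results do not depend on the start-day distribution: every hold starting on Day 1 is missed, and so is every hold of 20 days or more. The 8/21 and 15/21 figures rest on uniform start days. All of the figures assume one hold per subject, otherwise full dosing on Days 1-21 and no off-schedule dose on Days 22-28.

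The consequence is an undercount of interruption episodes, and of their reasons, in a descriptive exposure table. It does not reach ORR, PFS or the sample size. The change is worth making because the rule as stated works against the holds of most interest and is easy to replace.

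**What to change.** In SAP 7.4.1.2:

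1. Define a computed lenalidomide interruption as two or more consecutive scheduled days without a dose. Scheduled days are Days 1-21 of the fixed cycle calendar, from first lenalidomide dose to permanent discontinuation or data cut-off.
2. Treat Days 22-28 as unscheduled, and count a hold that crosses cycles as one episode until the next dose.
3. State an analysis tolerance at cycle start, so that a visit within the window is not counted as a hold.
4. Derive the episodes from the eCRF page Record of Study Medication - lenalidomide, which the SAP already uses for reductions, and take only the reason from the dose modification page.
5. State that the table counts computed interruptions, and add a by-subject listing of all reported interruptions whether or not computed, as for elotuzumab delays.

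The cost is SAP wording, one derivation from dosing data the SAP already uses, and one listing. The reported number of interruptions will rise. The tolerance will leave some brief holds at cycle start out of the count; those that were reported will appear in the listing. No dosing or clinical rule changes.
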